6. STUDY ASSESSMENTS AND PROCEDURES

Study procedures and assessments are summarized in the Schedule of Assessments and in Section 7. Adherence to the study design requirements, including those specified in the Schedule of Assessments (Table 1) are essential and required for study conduct. Protocol waivers or exemptions are not allowed, except for immediate safety concerns.

6.1. Medical History, Demography, and Baseline Characteristics

6.1.1. Medical History

Medical history will be collected to ensure subjects are eligible for participation in the study (per inclusion [Section 4.2] and exclusion [Section 4.3] criteria).

Data collected will include year of plaque psoriasis diagnosis, CV medical history and risk factors (including height, weight, blood pressure (BP), smoking history, medical conditions, and family history of premature CV disease) and family history of liver disease.

6.1.2. Demographics

Demographic information collected will include age, sex, race, and ethnicity.

6.1.3. Baseline Characteristics

During Screening, single 12-lead electrocardiograms (ECGs) will be obtained using an ECG machine that automatically calculates the heart rate (HR) and measures PR, QRS, QT, and QTcF intervals. Subjects should be in a supine or semi-recumbent position for at least 5 minutes before ECG is measured.

Holter monitoring will be conducted for approximately 13 hours on Days -1, 1 and 29, and approximately 1 hour on Days 2 and 30 to collect pre-treatment and time-matched ECG data.

6.2. Psoriasis Disease Assessments

6.2.1. Physician Global Assessment

The PGA is a clinical tool for assessing the current state/severity of a subject's psoriasis at a given time point. It is a static 5-point morphological assessment of overall disease severity, as determined by the Investigator, using the clinical characteristics of erythema, scaling, and plaque thickness/elevation as guidelines; higher PGA scores represent more severe disease. The BSA affected is not considered in scoring of the PGA (see Section 6.2.2 for details on BSA scoring). Variations of the PGA are frequently used in clinical studies because it is a simple assessment that is more similar to the assessments actually used in clinical practice (see Appendix 1 for details). The PGA should be performed first, prior to %BSA, PASI, and Local Tolerability Scale (LTS) assessments.

6.2.2. Body Surface Area Affected

The assessment of the %BSA affected is an estimate of the percentage of total involved skin with psoriasis. For the purpose of clinical estimation, the total palmar surface of the subject's palm (including fingers) may be assumed to be approximately equivalent to 1% BSA. The %BSA affected by psoriasis will be evaluated (from 0 to 100%). Details on calculation of approximate %BSA involvement in each subject (total and individual areas) are provided in Appendix 2. %BSA is a static assessment made without reference to previous scores. Note that plaques on the scalp, palms, and soles should be excluded from the %BSA calculations used to determine eligibility.

6.2.3. Psoriasis Area and Severity Index

The PASI scoring system is a widely used standard clinical tool for assessing the severity of psoriasis that takes into account the overall severity of erythema (redness), induration (plaque thickness), and scale, and the extent of %BSA affected with psoriasis. The 3 clinical signs are each graded on a 5-point scale (0 to 4) and the %BSA affected is scored on a 7-point scale (0 to 6) for each of the 4 specified body regions (head, upper extremities, trunk, and lower extremities). The individual scores are multiplied by a weighted factor for each body region; the sum of these scores gives the overall PASI score. Higher scores indicate more severe disease. PASI is a static assessment made without reference to previous scores. Details on PASI calculation are provided in Appendix 2.

6.3. Safety Assessments

6.3.1. Adverse Events

All AEs will be collected from the time the subject signs the ICF until the final visit/contact with the subject. Additional safety information, including the definition of an AE and the methods for recording, evaluating, and assessing causality of AEs and the procedures for completing and transmitting SAE reports are provided in Section 8.

6.3.2. Brief Physical Exam

A brief physical examination will include, at a minimum, assessments of the skin, lungs, CV system, and abdomen (liver and spleen). Height and weight will be measured at Screening only. Investigators should pay special attention to clinical signs related to previous serious illness.

6.3.3. Vital Signs

Vital signs will be measured before blood collection for clinical laboratory assessments and PK analysis (where applicable) and will include measurement of systolic and diastolic BP, HR, and body temperature. Subjects should be in a supine or semi-recumbent position for at least 5 minutes before vital signs measurement.

6.3.4. Clinical Safety Laboratory Assessments

All protocol-required laboratory assessments must be conducted in accordance with the Study Reference Manual or Laboratory Manual and the protocol Schedule of Assessments (Table 1). Laboratory requisition forms must be completed, and samples must be clearly labeled with the subject number, protocol number, site/center number, and visit date. Details for the preparation and shipment of samples will be provided by the laboratory and are detailed in the Study Reference Manual or the Laboratory Manual. Reference ranges for all safety parameters will be provided to the site by the laboratory responsible for the assessments.

A list of clinical laboratory tests and parameters is provided in Table 3.

All laboratory tests with values that are considered clinically significantly abnormal during participation in the study should be repeated until the values return to normal or Baseline. If such values do not return to normal within a period judged reasonable by the Investigator, the etiology should be identified, if possible, and the Sponsor notified.

Table 3: Laboratory Tests

Diagnostic Screening Tests								
HBsAg Pregnance	 HBsAg Pregnancy Tests: (serum at Screening and urine at other visits; WOCBP only) 							
HBC antibody FSH (as	FSH (as needed in women of non-childbearing only)							
Anti-HBc At the Investigator's discretion, subjects may be screened for alcohol and illicit drug use.								
Serum Chemistry								
• BUN	 Total carbon dioxide 	 Uric acid 						
Creatinine	• Calcium	 Total bilirubin 						
Glucose (fasting not required)	• AST	(+fractionated if						
• Sodium	• ALT	required)						
Potassium	 Alkaline phosphatase 	Total protein						
Chloride		 Albumin 						
Hematology								
Platelet count	• RBC Indices:	WBC Differential:						
RBC count	MCV	Neutrophils						
WBC count (absolute)	MCH	Lymphocytes						
Reticulocyte count	MCHC	Monocytes						
Hemoglobin	Reticulocyte percentage	Eosinophils						
Hematocrit		Basophils						
Routine Urinalysis								
Specific gravity	• Dipstick:							
Microscopic examination	pH							
(if blood or protein is abnormal	Glucose							
abnormai	Protein							
	Blood							
	Ketones							

Abbreviations: ALT = alanine aminotransferase; Anti-HBc= anti-hepatitis B core antigen; AST = aspartate aminotransferase; BUN = blood urea nitrogen; FSH = follicle-stimulating hormone; HBC = hepatitis C virus; HBsAg = hepatitis B surface antigen; HIV = human immunodeficiency virus; MCH = mean corpuscular hemoglobin; MCHC = mean corpuscular hemoglobin concentration; MCV = mean corpuscular volume; RBC = red blood cell(s); WBC = white blood cell(s); WOCBP = women of childbearing potential.

6.3.6. Local Tolerability Scale

At each specified study visit, the Investigator (or qualified evaluator) will assess the presence and overall degree of irritation at the application sites, according to the LTS (an example of the LTS is provided in Table 4). The score will ideally represent an 'average' across all application sites. To the fullest extent possible, the same Investigator (or designated evaluator) will perform all tolerability assessments for an individual participant throughout the study. If the subject is applying study treatment to "sensitive areas" (e.g., genitals, face, neck, and skin folds), a separate LTS will be used to assess the degree of irritation for these areas.

Table 4: Grading Scale for Local Tolerability

Score	Severity	Description			
0	No irritation	ation No evidence of local irritation/intolerance			
1	Mild	Minimal erythema and/or edema, slight glazed appearance			
2	Moderate	Definite erythema and/or edema with peeling and/or cracking but does not require treatment modification			
3	Severe	Erythema, edema glazing with fissures, few vesicles or papules			
4	Very Severe	Strong reaction spreading beyond the treated area, bullous reaction, erosions			

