1.3.3. Overall Benefit Risk

Taking into account the measures taken to minimize risk to subjects in this study, the potential risks identified in association with tapinarof are justified by the anticipated benefits that may be afforded to subjects with psoriasis.

OBJECTIVES AND ENDPOINTS 2.

The objectives and associated endpoints of the study are as follows:

Objectives	Associated Endpoint
Primary	Primary
To evaluate the safety and tolerability of topical tapinarof cream, 1% in adult subjects with extensive plaque psoriasis	 Frequency and severity of AEs (local and systemic) Laboratory and biomarker values Vital signs ECGs Mean Local Tolerability Scale scores by visit
To evaluate the PK of topical tapinarof cream, 1% in adult subjects with extensive plaque psoriasis	 Tapinarof and tapinarof sulfate (metabolite) plasma PK parameters on Day 1 and Day 29, if data permit, including: AUC_{0-τ} C_{max} t_{max} t_{1/2}
Secondary	Secondary
To exclude clinically relevant effects of tapinarof cream, 1% on QTcF	 Analysis of ΔQTcF at each post-treatment time point on the sampling day with the higher C_{max} (Day 1 or Day 29) Concentration-QTc analysis investigating the relationship between tapinar of plasma concentration and ΔQTcF, if data permit
To assess the efficacy of tapinar of cream, 1% in adult subjects with extensive plaque psoriasis	 Mean change from Baseline to Day 29 in PGA, PASI, and %BSA
Exploratory	Exploratory

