8.1.4. Adverse Events of Special Interest

In prior clinical studies, the following AEs have been identified as AEs of particular clinical importance and will be reported as AESIs in this study; in each case study drug may be discontinued, based upon Investigator's judgment, and the subject may be discontinued from the study.

- Contact dermatitis: the study site should collect location, duration, size, associated symptoms (itching, burning, pain), severity (mild, moderate, or severe), and photograph the affected site (if possible). If subject contacts the study site to report significant skin irritation at or near the site of study drug application between study visits, the subject should be brought for an unscheduled visit, if possible.
- Folliculitis: the study site should collect the location, duration, size, associated symptoms (itching, burning, pain), severity (mild, moderate, or severe), indicate whether pustular, and photograph the affected site (if possible).
- Headache: site should collect duration, severity (mild, moderate, or severe), onset, and location.

For each AESI, a narrative may be written and included in the Clinical Study Report.

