### 6. GENERAL ANALYSIS CONSIDERATIONS

The statistical analyses will be reported using summary tables, listings, and figures (TLFs). The International Council for Harmonisation (ICH) numbering convention will be used for all TLFs.

Continuous variables will be summarized with means, standard deviations, medians, minimums, and maximums. Categorical variables will be summarized by counts and by percentage of subjects in corresponding categories. Percentages are based on the number of non-missing results unless otherwise mentioned. Percentages showing a rate relative to the total number of subjects in this group are given in special tables (e.g., AE tables). Footnotes will specify the percent basis in those cases.

All analyses and tabulations will be performed using SAS® software Version 9.4 or higher. Tables, listings, and figures will be presented in RTF format.

The process for SAS program validation and quality control (QC) for programs and outputs is documented in the Synteract working instruction "SAS programming quality control." Study-specific QC requirements can be found in Appendix B: SAS Programming QC Requirements.

Unless otherwise specified, the Baseline value for each variable is the last non-missing value prior to the initiation of study drug. No imputations will be made for missing values. Summaries will be based on observed data only. Unscheduled visits will not be summarized but will be included in the listings.

Conventions for handling partial dates and missing dates for AEs and prior and concomitant medications are given below. Listings will present the dates in their original format (without any imputation).

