### **10.7 Local Tolerability Scale**

Local tolerability scale (LTS) overall score for dryness, erythema, and peeling will be summarized using descriptive statistics at Baseline and at Days 15 and 29 as will the number and percent of subjects who apply study drug to the following sensitive areas: face, neck, skin folds, axilla, inframammary, anal crux, and genitalia. If 5 more subjects treat a sensitive area(s) at any time during the treatment period, LTS scores will be summarized at Baseline and Days 15 and 29 for that specific area(s).

In addition, LTS scores will be listed by subject overall and by sensitive area as applicable.

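### Outside sensitive areas the LTS is a rater's average over all application sites, reported as visit means, so a small severe focal reaction can score near zero in this one primary tolerability endpoint

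*Protocol*

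**What the plan says.** **The score.** Protocol 6.3.6 has the investigator or a qualified evaluator give one overall irritation score across application sites: "The score will ideally represent an 'average' across all application sites". No weighting or rounding rule is given. Table 4, offered as an example of the scale, runs from 0 to 4. Its top grade reads "Strong reaction spreading beyond the treated area, bullous reaction, erosions", and grade 3 includes fissures and a few vesicles or papules. For sensitive areas such as genitals, face, neck and skin folds, "a separate LTS will be used to assess the degree of irritation for these areas".

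**The endpoint.** Protocol Section 2 lists "Mean Local Tolerability Scale scores by visit" among the primary safety and tolerability endpoints. The frequency and severity of AEs, local events included, stands in the same list.

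**Timing and summary.** The Schedule of Assessments places the LTS on Days 1, 15 and 29. SAP 10.7 says the scores, which it names as dryness, erythema and peeling, "will be summarized using descriptive statistics at Baseline and at Days 15 and 29". A sensitive area gets its own table only if about 5 subjects treat it; otherwise its scores are listed.

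**Other visits.** SAP 6 states: "Unscheduled visits will not be summarized but will be included in the listings". Under the contact dermatitis item of Protocol 8.1.4, a subject who reports significant irritation between visits is called in: "the subject should be brought for an unscheduled visit, if possible". That item collects location, size, severity and, if possible, a photograph, but does not ask for an LTS score. The Follow-up/Early Termination list in Protocol 7.10 has no LTS either.

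**The concern.** The signs that define grades 3 and 4 can be confined to a small patch, yet the score describes all treated skin, and entry requires at least 20% BSA involvement. The endpoint then averages over about 20 subjects. Both steps pull an isolated severe reaction toward zero, most of all in a maximal-use population with large treated areas.

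There are only two post-baseline assessments, 14 days apart. A reaction that arises and settles between them has no planned LTS score. A subject who stops because of a local reaction gives none at Early Termination, and SAP 6 uses observed data without imputation, so that subject simply leaves the later visit means.

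At stake is whether the one scheduled, structured irritation measure can show the kind of reaction its upper grades describe. Protocol 1.1.2 says the study is meant to support registration.

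**Working it through.** The plan states no figure to reproduce: the sample size rests on feasibility, and the LTS has no threshold, margin or decision rule. The check is arithmetic on the documents' own inputs.

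**Inputs**
- Grades 0 to 4 (Protocol Table 4).
- Minimum affected area at entry: 20% BSA (Protocol 4.2).
- One handprint is about 1% BSA (Protocol Appendix 2).
- About 20 subjects (Protocol 4.1).
- Assumed: the average is weighted by area, and treated skin outside the reaction is at grade 0.

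**Step 1: one subject's score**

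Score = grade × reacting handprints / treated handprints.

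| Treated BSA | Reacting handprints | Grade 3 | Grade 4 |
|---|---|---|---|
| 20% | 1 | 3×1/20 = 0.15 | 4×1/20 = 0.20 |
| 20% | 2 | 0.30 | 0.40 |
| 20% | 5 | 0.75 | 1.00 |
| 20% | 10 | 1.50 | 2.00 |
| 30% | 1 | 0.10 | 0.13 |
| 50% | 1 | 0.06 | 0.08 |

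If the score were also rounded to a whole grade (not specified), it would reach 1 once the average is 0.5. That needs 0.5/3 = 16.7% of the treated area at grade 3, or 0.5/4 = 12.5% at grade 4. On 20% BSA this is about 3.3 or 2.5 handprints.

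**Step 2: other readings of the average**
- Equal weight to four body regions, one region at grade 3 or 4 and the rest at 0: 3/4 = 0.75 or 4/4 = 1.00.
- Area weighting with the remaining skin at grade 1, one handprint on 20% BSA: 0.15 + 0.95 = 1.10, or 0.20 + 0.95 = 1.15. The severe patch adds only 0.10 or 0.15 to a score that would otherwise be 1.

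The score therefore depends on which reading the rater adopts, and about 6 sites will be rating.

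**Step 3: the visit mean**

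One affected subject of 20, one handprint on 20% BSA, all others at 0: 0.15/20 = 0.0075 or 0.20/20 = 0.01. If the worst-site grade were recorded instead, the same subject would move the mean by 3/20 = 0.15 or 4/20 = 0.20. A mean hides much of the event even then; a count by grade does not.

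**Step 4: the sensitive-area table**

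Reading the SAP threshold as 5 or more, the binomial chance that at least 5 of 20 subjects treat a given area is 0.3%, 4.3%, 17% and 58.5% for assumed treatment rates of 5%, 10%, 15% and 25%. Below the threshold, the separate scores appear only in listings.

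**The case against.** The strongest reply is that severe local reactions already have a route to the tables. AE frequency and severity is also primary. Protocol 8.1.1 includes application-site tolerability among AE events and asks whether a skin event is spreading. SAP 10.4 tabulates TEAEs by highest severity per subject, counts missing severity as severe, and lists contact dermatitis separately. This stands. It limits the point to the LTS endpoint. It does not close the gap, because AE reporting depends on the investigator's judgement, signs of the studied disease count as AEs only if more severe than expected, and no LTS grade triggers an AE report.

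Three stronger readings are tempting, and the documents do not support them:
- **That the primary tolerability result tends to zero whether or not the cream irritates.** Widespread irritation raises an average over sites: ten of 20 handprints at grade 3 gives 1.50. The LTS mean is also only one of several primary endpoints.
- **That leaving unscheduled visits out of summaries discards LTS scores.** No LTS is requested at those visits, so no planned score is lost. The visits are listed, and an AE found there enters the AE tables.
- **That a focal reaction would be recorded as 0.** The protocol describes an overall degree of irritation that is ideally an average, which may be a global judgement. The grade 4 wording on spread beyond the treated area fits poorly with averaging it away.

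Some safeguards also exist. The SAP's descriptive statistics include the maximum, LTS scores are listed by subject, and Protocol 10.4.2 foresees frequency tables for categorical safety data. But the maximum is the highest subject-level average at a visit, not the worst site, and SAP 10.7 names no table of counts by grade.

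**Conclusion.** The point holds in a limited form. Outside the sensitive areas, the planned LTS tables cannot show the worst application site or a subject's worst post-baseline grade, and a small severe focal reaction can score near zero. Under area weighting with the rest of the skin clear, one handprint at grade 3 or 4 scores 0.15 or 0.20 on 20% treated BSA and 0.06 or 0.08 on 50%. Under regional averaging, one region at grade 3 or 4 scores 0.75 or 1.00, so near zero is a possible result and not a general one. The undefined average is part of the defect.

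The size rests on three assumptions that the protocol neither states nor excludes: area weighting, a reaction of a few handprints at most, and otherwise unirritated skin. The effect is confined to the LTS endpoint. A reaction reported as an AE is still counted by severity. This is a worthwhile, inexpensive improvement to a descriptive endpoint, not a failure of the study's safety assessment.

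**What to change.** - **Protocol 6.3.6:** keep the overall score and say how the average is formed. Add a worst-application-site grade by the same rater at each LTS visit, at any unscheduled visit for skin irritation, and at Early Termination. Carry the additions into Table 1 and Sections 7.10 and 8.1.4.
- **SAP 10.7:** beside the mean, tabulate each subject's worst post-baseline grade as counts and percentages by grade. Include unscheduled and Early Termination assessments, as a stated exception to the general rule in SAP 6.
- **Reconcile the scales:** Protocol Table 4 has a single 0-4 irritation scale, while SAP 10.7 and its table list summarize dryness, erythema and peeling. The documents should say which is collected and how one relates to the other, since fissures, vesicles, bullae and spread are not named in the SAP.

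**Cost:** about one eCRF field and one table, with no added scheduled visits, but a short extra assessment at unscheduled irritation visits and at Early Termination. The field count is an estimate because the eCRF is not among the documents. The tolerability profile may look less favourable.

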6.3.7. Continuous Holter Monitoring

The 12-lead Holter and ECG equipment will be supplied and supported by ERT. All ECG data will be collected using a Global Instrumentation (Manlius, NY, USA) M12R ECG continuous 12-lead digital recorder. The continuous 12-lead digital ECG data will be stored onto secure digital memory cards. ECGs to be used in the analyses will be selected by pre-determined time points as defined in the Schedule of Assessments (Table 1) and will be read centrally by ERT.

The following principles will be followed in ERT's core laboratory:

- ECG analysts are blinded to the subject number and visit;
- Baseline and on-treatment ECGs for a particular subject will be over-read on the same lead and will be analyzed by the same reader;
- The primary analysis lead is lead II. If lead II is not analyzable, then primary lead of analysis will be changed to another lead for the entire subject data set.

The following is a brief description of ECG analysis methods utilized by ERT's core laboratory:

TQT Plus ECG Extraction Technique

• Ten 14-second digital 12-lead ECG tracings will be extracted from the continuous Holter recordings using the 'Thorough QT Plus method,' a computer-assisted and statistical process utilized by ERT. The method enables extraction of ECGs with the lowest HR variability and noise within the protocol-specified extraction time window (e.g., the HR and QT changes from beat-to-beat in the range of < 10%). At each protocol-specified time point, 10 ECG replicates will be extracted from a 5-minute "ECG window" (typically, the last 5 minutes of the 15-minute period when the subject is maintained in a supine or semi-recumbent quiet position).

Expert-Precision QT Analysis

- Expert-precision QT analysis will be performed on all analyzable (non-artifact) beats in the 10 ECG replicates. Statistical quality control procedures are used to review and assess all beats and identify "high" and "low" confidence beats using several criteria, including:
 - o QT or QTc values exceeding or below certain thresholds (biologically unlikely);
 - o RR values exceeding or below certain thresholds (biologically unlikely);
 - o Rapid changes in QT, QTc or RR from beat to beat.
- Measurements of all primary ECG parameters (QT, QTc, RR) in all recorded beats of all replicates that are deemed "high confidence" are performed using COMPAS software. All low confidence beats are reviewed manually and adjudicated using pass-fail criteria. The final QC assessment is performed by a cardiologist. The beats found acceptable by manual review are included in the analysis. The median QT, QTc, and RR values from each extracted replicate are calculated, and then the mean of all available medians from a nominal time point is used as the subject's reportable value at that time point.

- Categorical T-wave morphology analysis and the measurement of PR and QRS intervals will be performed manually in 3 of the 10 ECG replicates at each time point. Each fiducial point (onset of P-wave, onset of Q-wave, offset of S-wave, and offset of T-wave) is electronically marked.
- For T-wave morphology and U-wave presence, treatment-emergent changes will be assessed, i.e., changes not present at Baseline. For each category of T-wave morphology and U-waves, the category will be deemed as present if observed in all replicates at the time point. For Baseline, the category will be deemed as present if observed in all replicates from all time points that constitute Baseline. The T-wave morphology categories are described as follows:

Category	Description
Normal T-wave	Any positive T-wave not meeting any criterion below
Flat T-wave	T amplitude < 1 mm (either positive or negative) including flat isoelectric line
Notched T-wave (+)	Presence of notch(es) of at least 0.05 mV amplitude on ascending or descending arm of the positive T-wave
Biphasic	T-wave that contains a second component with an opposite phase that is at least 0.1 mV deep (both positive/negative and negative/positive and polyphasic T-waves included)
Normal T-wave (-)	T amplitude that is negative, without biphasic T wave or notches
Notched T-wave (-)	Presence of notch(es) of at least 0.05 mV amplitude on descending or ascending arm of the negative T-wave
U-waves	Presence of abnormal U-waves

